## 4.2 Exclusion criteria

Patients fulfilling any of the following criteria are not eligible for inclusion in this study. No additional exclusions may be applied by the investigator, in order to ensure that the study population will be representative of all eligible patients.

1. Any medical or neurological condition other than AD that could explain the patient's dementia (e.g., abnormal thyroid function tests, vitamin B12 or folate deficiency, posttraumatic conditions, syphilis, head injury, Huntington's disease, Parkinson's disease, subdural hematoma, normal pressure hydrocephalus, brain tumor) at baseline;
2. A current diagnosis of probable or possible vascular dementia according to the National Institute of Neurological Disorders and Stroke and the Association Internationale pour la Recherche et l'Enseignement en Neurosciences criteria (NINDS-AIREN) at baseline;
3. A current DSM-IV diagnosis of major depression, unless successfully treated with a stable dose of an antidepressant without anticholinergic properties for at least 4 weeks at baseline;
4. Any other DSM-IV Axis 1 diagnosis that may interfere with the evaluation of the patient's response to study medication, including other primary neurodegenerative dementia, schizophrenia, or bipolar disorder at baseline;
5. A current diagnosis of active, seizure disorder at baseline;

6. A history or current diagnosis of severe cerebrovascular disease (e.g., stroke, transient ischemic attacks, aneurysms) at baseline;
7. A current diagnosis of severe or unstable cardiovascular disease (e.g., cardiac failure congestive, angina unstable), hypertension, diabetes at baseline;
8. A current diagnosis of bradycardia (< 50 bpm), sick-sinus syndrome, or conduction defects (sino-atrial block, second or third degree atrio-ventricular block) at baseline;
9. A current diagnosis of acute, severe, or unstable asthmatoïd conditions (e.g., severe chronic obstructive pulmonary disease (COPD) at baseline;
10. A current diagnosis of active, uncontrolled peptic ulceration or gastro-intestinal bleeding within the last 3 months from baseline;
11. Clinically significant urinary obstruction at baseline;
12. Patients with extrapyramidal disorders (e.g., Parkinson's disease, Parkinson's syndrome).
13. Patients with complication of gastrointestinal adverse events such as nausea and vomiting during oral ChE inhibitors treatment except for such gastrointestinal adverse events if it is apparent to be caused by other than oral ChE inhibitors;
14. Patients with low body weight as judged by the investigators
15. Current diagnosis of an active skin lesion/disorder that would influence to the adhesion and potential skin irritation of the patch (e.g., atopic dermatitis, wounded or scratched skin in the area of the patch application) at baseline;
16. A disability that may prevent the patient from completing all study requirements (e.g., blindness, deafness, severe language difficulty) at baseline ;
17. Patients with a history of hypersensitivity to any ingredients of rivastigmine or carbamate derivatives;
18. Patients who have taken rivastigmine any time in the past;
19. Significantly change of content and frequency of rehabilitation, day care, day service during the 4 weeks prior to efficacy assessment at baseline;
20. Taken any investigational drug (including investigational biologics) in the 90 days prior to baseline or within 5 half-lives of the compound, whichever is longer;
21. Taken any of the following treatments (Potential topical or ophthalmic formulations of the following compounds will be allowed)
  - donepezil > 5 mg/day 4 weeks prior to baseline (Visit 2);
  - Any ChEIs (except for donepezil, galantamine), selegiline, centrally acting anticholinergic drugs, olanzapine or tricyclic and tetracyclic antidepressants during the 4 weeks prior to efficacy assessment at baseline;
  - Change of dosage and regimen of donepezil, galantamine, memantine (patients who have been on a stable dose of memantine during 4 weeks or more prior to efficacy assessment at baseline are allowed to enter the study and may continue to take memantine during the entire study without changing the dosage), psychotropic medication, antidepressants (except for tricyclic and tetracyclic antidepressants), anxiolytics (including benzodiazepine-type hypnotics), antiepileptics, drugs for Parkinson's disease, hypnotics (except for short-acting hypnotics such as zolpidem tartrate and zopiclone etc), agents which improve cerebral circulation/metabolism, vitamin E and estrogens and peripheral anticholinergic agents (except for oxybutynin

hydrochloride and propiverine hydrochloride, tolterodine tartrate, solifenacin and imidafenacin etc), Yokukan-san, Yokukansankachimpahange during the 4 weeks prior to efficacy assessment at baseline;

- Succinylcholine-type muscle relaxants, lithium during the 2 weeks prior to efficacy assessment at baseline;
- Newly used benzodiazepine-type hypnotics of short duration, newly used or irregularly used zolpidem tartrate and zopiclone within 24 hours prior to efficacy assessment at baseline;

22. Result(s) of laboratory tests at the screening visit:

- total bilirubin 3.0 mg/dL or above;
- AST (GOT) and/or ALT (GPT) 3  $\times$ ULN or above;
- serum creatinine 2.0 mg/dL or above;

23. History of malignancy of any organ system, treated or untreated, within the past 5 years whether or not there is evidence of local recurrence or metastases, with the exception of localized basal cell carcinoma of the skin;

24. Patients who, in the opinion of the investigator, will be otherwise unsuitable for inclusion in this clinical study (e.g., an advanced, severe, progressive, or unstable disease of any type that may interfere with efficacy and safety assessments or put the patient at special risk);

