5.2 Rule of exclusion criteria of analysis sets

The protocol deviations defined for this study are the followings:

Table 1 Protocol deviations that cause patients to be excluded

Deviation Code	Text Description	Severity/ Analysis Classify action Code
E01	Any medical or neurological condition other than AD that could explain the patient's dementia at baseline.	1
E02	Current diagnosis of probable vascular dementia according to National Institute of Neurological Disorders & Stroke and AIREN criteria at baseline.	1
E03	A current DSM-IV diagnosis of major depression, unless successfully treated with a stable dose of an antidepressant without anticholinergic properties for at least 4 weeks at baseline	49
E04	Any other DSM-IV Axis1 diagnosis interfering with evaluation of patient's response to study medication including other primary neurodegenerative dementia, schizophrenia or bipolar disorder at baseline.	49
E05	A current diagnosis of active, seizure disorder at baseline	49
E06	A history or current diagnosis of severe cerebrovascular disease at baseline	49
E07	A current diagnosis of severe or unstable cardiovascular disease, hypertension, diabetes at baseline	49
E08	A current diagnosis of bradycardia (< 50 bpm), sick-sinus syndrome, or conduction defects (sino-atrial block, second or third degree atrio-ventricular block) at baseline	49
E09	A current diagnosis of acute, severe, or unstable asthmatoïd conditions at baseline	49
E10	A current diagnosis of active, uncontrolled peptic ulceration or gastro-intestinal bleeding within the last 3 months from baseline	49
E11	Clinically significant urinary obstruction at baseline	49
E12	Patients with extrapyramidal disorders	49
E13	Patient with complication of gastrointestinal (GI) adverse events during oral ChE inhibitors treatment except for GI adverse events caused by drugs other than oral ChE inhibitors	49
E14	Patients with low body weight as judged by the investigators at Visit 1 and/or 2 date	49
E15	Current diagnosis of an active skin lesion/disorder that would influence to the adhesion and potential skin irritation of the patch at baseline	49
E16	A disability that may prevent the patient from completing all study requirements at baseline	49
E17	Patients with a history of hypersensitivity to any ingredients of rivastigmine or carbamate derivatives	49

E18	Patients who have taken rivastigmine anytime in the past (Please consider partial dates)	49

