Analysis Set	PD severity codes that cause a subject to be excluded	Criteria that cause a subject to be excluded
FAS	0, 6, 8	Enrolled but no study drug received
PPS	0, 1, 6, 8	NA
SAF	8	

Table 3 Severity codes with action taken

Code	Action
0	Exclude from all efficacy analysis
1	Exclude from per protocol analysis
6	Exclude from Main Analysis Set

8	Exclude from all analysis
49	Report relevant protocol deviation – include in all analyses

5.3 SAS codes for statistical analyses.

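### In SAP 5.2 Table 1, row E04 keeps another primary neurodegenerative dementia in the per-protocol set (code 49), while the other wrong-dementia rows remove it (code 1) (minor)

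*Protocol*

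**What the plan says.** **Eligibility (Protocol 4.2).** Three exclusions matter here besides exclusion 1.

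- Exclusion 4 covers other interfering Axis 1 diagnoses, "including other primary neurodegenerative dementia, schizophrenia, or bipolar disorder at baseline".
- Exclusion 12 covers "Patients with extrapyramidal disorders" and gives Parkinson's disease as an example. Exclusion 1 also lists Parkinson's disease, among conditions that could explain the dementia.
- Exclusion 18 covers "Patients who have taken rivastigmine any time in the past", with no time limit.

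**Deviation codes (SAP 5.2 Table 1).**

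- E04 repeats the phrase, "including other primary neurodegenerative dementia, schizophrenia or bipolar disorder at baseline", with code 49.
- E01 reads "Any medical or neurological condition other than AD that could explain the patient's dementia at baseline" and has code 1. E02 (vascular dementia), I05 (no DSM-IV diagnosis of AD) and I06 (no probable AD by NINCDS-ADRDA) also have code 1.
- E12 (extrapyramidal disorders) has code 49. Rows E01 and E12 both leave out the protocol's examples.
- E18 (rivastigmine at any past time) has code 49. E21B (among others, cholinesterase inhibitors other than donepezil and galantamine, in the 4 weeks before the baseline efficacy assessment) has code 1.

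**Consequences (SAP 5.2 Tables 2 and 3).** Codes 0, 1, 6 and 8 remove a patient from the PP set; codes 0, 6 and 8 remove a patient from the full analysis set (FAS). Code 49 means "Report relevant protocol deviation – include in all analyses".

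**The concern.** A primary neurodegenerative dementia other than AD is a condition other than AD that could explain the patient's dementia. E04 and E01 therefore describe the same patient but prescribe opposite actions. E04 is the outlier: the SAP treats a wrong dementia diagnosis as a reason for PP exclusion in E01, E02, I05 and I06. The likely cause is that E04 combines a wrong-dementia diagnosis with psychiatric diagnoses such as schizophrenia and bipolar disorder.

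SAP 5.2 does not say whether a deviation is recorded once or under every row it meets. PP membership can then depend on filing practice, and two patients with the same condition can be handled differently. The PP set is meant to show the MMSE change in AD patients who had only 1-step titration and no major deviation (SAP 2.2), so a patient with a different dementia does not belong in it. The study is open-label and single-arm, which is a further reason to settle such choices before database lock.

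**Working it through.** **1. Set membership by recorded row.** The rule is SAP 5.2 Table 2: a patient leaves a set if any recorded code is on that set's exclusion list (FAS: 0, 6, 8; PP set: 0, 1, 6, 8).

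| Rows recorded | Codes | FAS | PP set |
|---|---|---|---|
| E04 only | 49 | in | **in** |
| E04 and E01 | 49, 1 | in | **out** |
| E04, I05 and I06 | 49, 1, 1 | in | **out** |
| E12 only | 49 | in | in |
| E12 and E01 | 49, 1 | in | out |
| E18 only (use more than 4 weeks before baseline) | 49 | in | in |
| E18 and E21B (use within 4 weeks) | 49, 1 | in | out |

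The first three lines can describe one and the same patient, and the result depends only on which rows are filed. The two E12 lines differ by a clinical fact, namely whether the Parkinson's disease could explain the dementia. The two E18 lines differ by the time of use. No line changes the FAS.

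**2. Where the PP set is used.** SAP 2.5.4 item 1 uses it for MMSE change at Week 24, SAP 2.6.1 for MMSE change at Week 8, and SAP 4 item 1 for the MMSE responder rate. The opening sentence of 2.6.1 speaks of all secondary efficacy variables that follow, but only MMSE at Week 8 follows there. QOL-AD, NPI-10 change and Modified Crichton change are specified for the FAS (SAP 2.8 and 2.9). J-CGIC (SAP 2.10) names no set.

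**3. Size.**

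- The planning SD is 3.0 (Protocol 9.8, SAP 3). The plan's own figure reproduces: n = (1.96 × 3.0 / 0.6)² = 96.04, rounded up to 97.
- The documents give neither the size of the PP set nor the number of affected patients. Assumptions: PP size n of 60 to 90; k affected patients (1 to 3); each differs from the others by d = 3.0 points (one SD), all in the same direction.
- Shift of the PP mean = k × d / n.
  - k = 1: 3.0/90 = 0.03 to 3.0/60 = 0.05.
  - k = 3: 9.0/90 = 0.10 to 9.0/60 = 0.15.
- 95% half-width of the PP mean = 1.96 × 3.0 / √n: 0.62 at n = 90 and 0.76 at n = 60.
- Even k = 3 is about 16% (0.10/0.62) to 20% (0.15/0.76) of the half-width.

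**The case against.** **One code-1 row is enough.** Table 2 removes a patient on any listed code, and a 49 beside it does not cancel the exclusion. A patient whose dementia has another neurodegenerative cause also meets E01, and meets I05 and I06 if the AD diagnosis fails. This stands. A reader might infer that every patient with another neurodegenerative dementia or with Parkinson's disease stays in the PP set; the documents support that only where E04 or E12 is the sole row filed. It does not remove the point, because the SAP has no rule that secures filing under every row.

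**Parkinson's disease.** Exclusion 1 concerns a condition that could explain the dementia; exclusion 12 concerns an extrapyramidal disorder whether or not it does so. Code 1 for the first and 49 for the second is coherent. This stands. Only Parkinson's disease that could explain the dementia falls under both rows, and there is no reason to recode E12 as a whole.

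**Earlier rivastigmine.** A reader might see a contradiction between E18 and E21B. The windows differ: E21B is limited to 4 weeks before the baseline efficacy assessment, and E18 has no limit. Use within 4 weeks is removed by E21B, and a different code for remote use is a choice open to the sponsor. What remains is that this choice has no stated reason, although rivastigmine is the study drug.

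**Reach.** A reader of the opening sentence of SAP 2.6.1 might infer that all secondary endpoints are affected. The sections on the individual endpoints do not bear this out.

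**Consequence.** PP results are supportive and their p-values descriptive, and eligibility is checked at both Visit 1 and Visit 2 (Protocol Table 6-1). This stands and keeps the point minor.

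**Conclusion.** There is a small, real inconsistency in SAP 5.2 Table 1. One condition, another primary neurodegenerative dementia, is coded 49 in E04 although the other wrong-dementia rows have code 1, and no rule on multiple filing resolves the overlap. The same gap applies to Parkinson's disease that could explain the dementia (E01 and E12). For E18 there is no contradiction, only an unexplained choice: a patient who used rivastigmine more than 4 weeks before baseline, with no other deviation, stays in the PP set.

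Only the supportive PP results on MMSE are affected, and the FAS primary analysis is unchanged. The likely shift is a few hundredths of a point per patient, under the assumed PP size and one-SD difference. Protocol 4.2 itself needs no correction. Severity: minor.

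**What to change.** In SAP 5.2, before database lock:

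1. Split E04: other primary neurodegenerative dementia with code 1, in line with E01, E02, I05 and I06; the remaining Axis 1 diagnoses keep code 49.
2. Add one sentence below Table 1: a deviation is recorded under every row it meets, and any code-1 row removes the patient from the PP set. Parkinson's disease that could explain the dementia is then filed under E01 as well as E12. E12 alone may keep code 49.
3. Recode E18 as 1, or give the reason for 49.

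The cost is a few table cells and one or two sentences, and possibly a few patients fewer in the PP set. No data collection, FAS analysis or sample-size figure changes.

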## 5 Treatment

### 5.1 Study treatment

#### 5.1.1 Investigational and control drugs

Rivastigmine transdermal patch will be supplied as marketed drugs (9 mg, 18 mg patch). Two different rivastigmine strengths 9 mg (5 cm^2) and 18 mg (10 cm^2) patch will be used in this study.

No control treatment is planned in this study.

**Table 5-1 Dosage form and drug content for 1 step titration**

| Form                            | Loading dose / Content per one patch | Size               |
|---------------------------------|--------------------------------------|--------------------|
| Exelon ® patch 9 mg  | 9 mg rivastigmine                    | 5 cm   |
| Exelon ® patch 18 mg | 18 mg rivastigmine                   | 10 cm  |

If patients cannot tolerate 1-step titration method to reach the maintenance patch dose of 18 mg/day, the investigators can use their clinical judgement to switch those patients to slower 3-step titration method in order to reach the maintenance dose of 18 mg/day or find the highest well-tolerated dose for each individual patient. Once the dose started at 4.5 mg of rivastigmine once a day, as a general rule, the dose should be increased to 4.5 mg a day at 4-week intervals to 18 mg once a day. Those patients will be allowed to stay in the study. Patients with doses below the planned dose will continue to participate in the study.

**Table 5-2 Dosage form and drug content for 3 step titration**

| Form                  | Loading dose / Content per one patch | Size                |
|-----------------------|--------------------------------------|---------------------|
| Exelon® patch 4.5 mg  | 4.5 mg rivastigmine                  | 2.5 cm  |
| Exelon® patch 9 mg    | 9 mg rivastigmine                    | 5 cm    |
| Exelon® patch 13.5 mg | 13.5 mg rivastigmine                 | 7.5 cm  |
| Exelon® patch 18 mg   | 18 mg rivastigmine                   | 10 cm   |

**5.1.2 Additional treatment**

Not Applicable.

**5.2 Treatment arms**

This is an open-label, single arm study; all of the patients will be assigned to 1-step titration treatment.

**5.3 Treatment assignment and randomization**

Not Applicable.

**5.4 Treatment blinding**

Treatment will not be blinded during the course of the study, as the study is open-label.

**5.5 Treating the patient**

Sponsor qualified medical personnel will be readily available to advise on trial related medical questions or problems.

**5.5.1 Patient numbering**

Each patient is uniquely identified in the study using 9-digit number which is combination of his/her 4-digit site number and a sequential 5-digit patient number. The site number is assigned by Novartis to the investigative site. Upon signing the ICF, the patient number is assigned a patient number by the investigator. At each site, the first patient is assigned the patient number 1, and subsequent patients are assigned consecutive numbers (e.g. second patient is assigned patient number 2, and third patient is assigned patient number 3). Once assigned to a patient, the Subject Number will not be reused. Upon signing the informed consent form, the patient is assigned the next sequential number as given by the investigator using the next blank eCRF available from the electronic data capture (EDC) system. If the patient fails to be registered for any reason, the reason for not being registered will be entered on the Screening Log, and the Demography CRF/eCRF should also be completed.

**5.5.2 Dispensing the study drug**

Each patient will purchase the drugs from the local pharmacy.

### **5.5.3 Handling of study and additional treatment**

#### **5.5.3.1 Handling of study treatment**

Upon receipt, all drugs should be stored according to the instructions specified on the drug labels. Patients will be asked to bring all unused drug and packaging at the end of the study or at the time of drug discontinuation for evaluating the drug compliance.

Treatment compliance will be investigated by Physician in one of the following categories:

- <25% Poor
- 25≤ ~<50% Average
- 50≤ ~<75% Good
- 75≤ ~≤100% Very good
- > 100% Reason to be specified (overdose or misuse)

In case of over compliance (> 100% reason to be specified, e.g. patients who ran out of their drug due to overdose or misuse), the investigators record the reason (overdose or misuse) separately on eCRF.

### **5.5.4 Instructions for prescribing and taking study treatment**

In general, one rivastigmine transdermal patch should be applied once daily by the caregiver on the back of the patient (alternatively, the patch can be applied to the upper arm or chest). The skin should be clean, and dry with no cuts, rashes, or other skin problems. The rivastigmine patch will be replaced every 24 hours and should be applied at approximately the same time. Additionally, the application site should be changed each time a new patch is applied to avoid skin irritation. When skin reactions appear, appropriate treatment including the use of topical steroids or topical antihistamines may be initiated. Also, other appropriate treatments including dose reductions, temporarily interruption or discontinuation of the treatment should be considered.

#### **Screening Period (Week -4 / -2 to -Day -1)**

During the screening period, patients will continue to receive donepezil or galantamine. At the baseline visit, patients discontinue previous treatment with donepezil or galantamine.

#### **Titration Period (Week 1 to 8)**

The day or following day (in case of a patient who takes his/her previous oral ChE inhibitors at the baseline visit) of the baseline visit (Day 1), all patients will start study treatment with one rivastigmine patch of 9 mg once a day. During the titration period, as a general rule, the dose should be increased to 18 mg once a day at 4 weeks later:

Week 1 – 4: Rivastigmine patch 9 mg/day

Week 5 – 8: Rivastigmine patch 18 mg/day

Should tolerability problems occur during the titration period, the dose can be adjusted in a range not exceeding 18 mg a day as appropriate depending on the clinical symptoms until the dose reaches the maintenance dose. In the event of gastrointestinal disorders (e.g., nausea, vomiting) or other tolerability problems, the dose should be reduced or treatment should be

temporarily interrupted until these adverse effects resolve. Patch treatment can be resumed at the same dose or previous well tolerated dose if interruption of treatment is around or within 4 days. Otherwise, treatment should be resumed at the initial starting dose (e.g. 4.5 mg or 9 mg). After treatment resumption, the dose at resumption should be maintained for a minimum of 2 weeks. If the dose is shown to be well-tolerated, the dose can be increased to the pre-resumption dose at intervals of 2 weeks or more.

Rivastigmine patch dose adjustments required for tolerability problems will be according to the dose adjustment scheme defines in [Section 5.5.5](#).

### **Maintenance Period (Week 9 to 24)**

The patients will be maintained on the maintenance dose of 18 mg/day rivastigmine patch at the time of Visit 4 (start of the maintenance period) and will undergo safety and efficacy assessments as per protocol. Patients not tolerating the 18 mg/day will stay on their highest tolerated dose in the study and will undergo safety and efficacy assessment as per protocol.

Decreasing the dose required for tolerability problems will be allowed at any time during the Maintenance Period and conducted according to the dose adjustment scheme defined in [Section 5.5.5](#).

After reducing the dose, investigators can try to increase up to dose of 18 mg/day according to the dose adjustment scheme defined in [Section 5.5.5](#).

All dosages prescribed to the patients and all dose changes during the study must be recorded to the Dosage Administration Record CRF (eCRF).

The investigator should promote compliance by instructing the patients and the caregivers to take the drug exactly as prescribed and by stating that compliance is necessary for the patient's safety and the validity of the study. The patient should be instructed to contact their investigators if he or she is unable for any reason to take the drug as prescribed.

